## 7.2 Data processing

Data will be collected at each centre, pseudonymised, and entered into a bespoke electronic case report form (eCRF). Completed forms will be submitted to the sponsor, ESAIC Clinical Trials Network (ESAIC CTN), in Brussels, Belgium.

## 7.3 Planned analyses

### 7.3.1 Main analysis

The aim of this research is to describe and quantify the epidemiology of the perioperative management of diabetic patients in Europe. Descriptive statistics such as mean (SD), median [interquartiles, range] and frequencies (%) will be presented as appropriate. The precision of the estimates will be reported with 95% confidence intervals to show the prevalence and incidence rates of diabetic phenotypes and major adverse events and complications.

The primary outcome measure is Days at Home at 30 Days (DAH-30).

Secondary outcomes include: Comprehensive Complications Index (CCI) score, based on Clavien-Dindo scale and the QoR-15 instrument measuring quality of recovery, taken only in patients who remain in hospital for Day 1 postoperative.

Secondary outcomes also include 30-day mortality, length of hospital stay, incidences of specific major adverse events (MI, MINS, AKI, PPC, CVA, PE, DVT and surgical site infection (SSI).)

Univariate analyses will be used to help identify variables of potential interest for multivariable analyses, in addition to stepwise selections. Robust multivariable regressions using maximum likelihood estimation (MLE), including Poisson and negative binomial, will be used to identify significant associations. Specific factors, or subsets of interest, will be investigated further using linear mixed models with MLE. Binary and categorical outcomes, such as occurrence of a postoperative pulmonary complication (PPC) will be analysed using multivariable logistic regression, survival analysis and Cox proportional hazards regression as appropriate.

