### 2.2 Risk categorisation

MOPED is a prospective cohort study asking patients to assent to documentation of their perioperative clinical course and progress, and a 10 minute follow-up telephone call, if discharged, at 30 days post surgery. No research related interventions are anticipated and all patients will receive routine care according to the standards laid out in each institution.

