### 3. OBJECTIVES, ENDPOINTS/OUTCOMES AND OTHER STUDY VARIABLES

#### 3.1 Objectives

1. To document, in a large scale observational, epidemiological study, the perioperative glycaemic management of established diabetic patients undergoing every type of surgery with anaesthesia in Europe.
2. To document the type, incidence and severity of all postoperative complications occurring up to 30 days postoperatively.
3. To document the impact of all complications by determining the number of days at home at 30 days (DAH-30, primary outcome), Comprehensive Complications Index (CCI) score, based on the Clavien-Dindo scale and other secondary outcomes.
4. To undertake sub-group analysis comparing these outcomes among:
  - DM1, DM2 and Other Diabetes ('Other' includes Maturity Onset Diabetes of the Young, (MODY) and LADA and any other type of diabetes).
  - Patients with different strata of pre-operative glycaemic control, i.e. HbA1c <53, HbA1c 53-69 and HbA1c >69 mmol. mmol;[11]
  - Patients who received different anaesthetic techniques:
    - Volatile versus total intravenous anaesthesia.
    - Regional versus general anaesthesia (GA) and
    - Patients receiving combined GA and regional anaesthesia versus GA alone.

A list of the a priori hypotheses is listed in Appendix 9.

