#### 3.2 Primary and secondary endpoint/outcome(s)

Primary endpoint: Days at Home at 30 days (DAH-30) [12,13]

Secondary endpoints:

Comprehensive Complications Index (CCI) score, based on Clavien-Dindo scale; [14,15]

Quality of Recovery scale (QoR-15), only taken from patients who are in hospital the day after surgery, i.e. Day 1 postoperatively [16], 30-day mortality,

Length of Stay in Hospital, Length of Stay in ICU if applicable.

Incidence of specific major adverse events as listed in European Perioperative Clinical Outcomes Definitions manuscript[18], (see Appendix 11 'Definitions of Outcomes') (MI, MINS, AKI, PPC, CVA, PE, DVT, AKI, Postoperative pulmonary infection (PPI));

Tertiary end-Points:

Intraoperative and postoperative management techniques of diabetes therapy will be documented, including fasting capillary/ABG blood glucose levels before, and <3hr after surgery. Also, peak blood glucose recorded during surgery, if available.

Also: incidence of diabetic ketoacidosis (defined as presence of the triad of: glucose > 12 mmol.L; ketonaemia > 3.0 mmol.L and lactaemia > 2.0 mmol.L);

Incidence and duration of use of IV Insulin Infusion Therapy.  
Incidence of hypoglycaemia (glucose < 4 mmol/l or severe < 2,5 mmol/l).

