### 4.3 Procedures

At screening day ("day -90" to "day of surgery", i.e. within 3 months of planned day of surgery), patients will be screened and be asked for consent (see 2.4). (see Appendix 2 'Patient Information Sheet' and Appendix 3 'Patient Consent Form'). For emergency surgery, diabetic patients' consent may be requested on the ward, immediately prior to coming to theatre on the day of surgery and up until hospital discharge.

If patients remain in hospital on the day of surgery, some data will be documented on the first day postoperatively (“Postop Day 1”), including QoR-15 quality of recovery score, taking 3-5 minutes.

Some patient data will also be recorded on Day of Discharge, provided the patient is discharged within 30 days of their surgery.

At Day 30 after surgery, data will be collected by telephone if the patient has been discharged. If still in hospital, patient data will be collected on the ward on Day 30.

There is some flexibility with the timing of data collection. Example: If Day of Discharge or follow-up Day 30 falls on a weekend, follow up may be conducted the next available working day. Similarly, if the patient cannot be contacted on Day 30, the patient should be contacted the next available day, e.g. Day 31. In this case, all outcomes recorded should be those that occurred up to and including Day 30 after surgery.

Table 1: Summary table of the timings of assessments

When	Action/Parameters Collected
Day-90 to Day 0	Screening Inclusion/Exclusion criteria Consent if elective Patient and diabetes baseline data Screening failure tracking SORT score
Day 0	Emergency patient screening and consent* Diabetes and patient baseline data if not already Surgical parameters SORT score Anaesthetic and PACU parameters
Day 1 Post-Op	QoR-15 Glucose and insulin parameters over 24 hr since surgery
Day of Discharge	Postoperative morbidity / complications CCI score
Day 30 Post-Op	DAH-30 (primary outcome) Mortality Postoperative morbidity / complications CCI score Length of Stay Diabetes parameters post surgery

\*Consent can be taken from patients undergoing emergency surgery up until the day of hospital discharge

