#### 6.5 Assessment of safety and reporting

The only study-related procedure in MOPED is the follow up call at 30 days (10 minutes) and for those in hospital on Day 1 postoperatively, the QoR-15 questionnaire (3-5 min). As such, the potential for serious events appears too remote to require their definition, assessment, or documentation.

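### MINS and AKI incidences will be rates of clinically detected events: testing follows local routine, and no text shown records who was tested

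*Protocol*

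**What the plan says.** **Endpoints.** Section 3.2 of the protocol names MINS and AKI under "Incidence of specific major adverse events as listed in European Perioperative Clinical Outcomes Definitions manuscript". Section 7.3.1 repeats them as "incidences of specific major adverse events (MI, MINS, AKI, PPC, CVA, PE, DVT and surgical site infection (SSI") and attaches 95% confidence intervals "to show the prevalence and incidence rates of diabetic phenotypes and major adverse events and complications".

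**Comparisons.** Section 3.1, objectives 2 to 4, documents complications and the other secondary outcomes. It then compares these outcomes by diabetes type, HbA1c stratum and anaesthetic technique. Section 7.3.4 lists subsets on the same three factors.

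**Measurement.** In Table 1 (Section 4.3), Day 1 holds the QoR-15 and glucose and insulin data. Complications are collected at discharge as "Postoperative morbidity / complications CCI score" and again at Day 30. Table 1 also has rows for DAH-30, mortality and length of stay, but no troponin or creatinine at any time point. The chart-extraction list in Section 6.4 names neither test and refers to the eCRF for details.

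**Testing practice.** Section 2.2 states: "No research related interventions are anticipated and all patients will receive routine care according to the standards laid out in each institution". Section 6.5 adds: "The only study-related procedure in MOPED is the follow up call at 30 days (10 minutes"), together with the Day 1 QoR-15 for inpatients.

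**Population.** Section 3.1 covers patients "undergoing every type of surgery with anaesthesia in Europe", while the List of Abbreviations spells out MINS as an injury after noncardiac surgery.

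**The concern.** MINS depends on a postoperative troponin, and AKI largely on creatinine. This is general clinical knowledge; the protocol's own definitions are in Appendix 11, which is not shown. A patient who was never sampled cannot be recorded as having MINS, whatever the truth. Chart review and questioning of the patient, which Section 6.2 gives as the sources for the CCI, cannot recover a value that nobody measured. A Day 30 call can pick up an event diagnosed elsewhere, but not an undiagnosed one.

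Two things follow. An incidence over all patients understates the true rate, and with 5,000 patients its interval will be narrow around the wrong value. And if one HbA1c stratum or anaesthetic group is sampled more often than another, it will show more MINS and AKI at equal true risk. The same would apply to centres or countries if these outcomes were examined that way. Sections 2.4 and 4.4 cite anecdotal evidence that management of emergency patients varies widely between nations and centres. Section 4.5 concludes that no significant risk of bias exists, but argues only from eligibility and does not consider how outcomes are detected.

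This goes beyond detail that can be left to the analysis plan. If testing status is not collected, no later analysis can recover it.

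**Working it through.** The protocol states no testing rate and no expected MINS or AKI rate, so there is no figure of its own to reproduce. The mechanism follows from the text; the sizes below are illustrations under stated assumptions.

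**Inputs**
- N = 5,000 (Section 7.1).
- Corrected significance level 0.0007 (Section 7.1).
- Assumed: true incidence p = 10% (range 5% to 20%); share tested t between 10% and 80%; untested patients counted as event-free.

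**1. All-patient incidence, testing unrelated to risk**

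Recorded incidence = p × t.
- 0.10 × 0.10 = 1%
- 0.10 × 0.40 = 4%
- 0.10 × 0.80 = 8%

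At t = 30%, true rates of 5% to 20% read 0.05 × 0.30 = 1.5% to 0.20 × 0.30 = 6%.

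**2. Apparent precision**

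Simple binomial half-width = 1.96 × √[r(1 − r)/5,000], where r is the recorded rate.
- r = 3%: 0.5 percentage points
- r = 10%: 0.8 percentage points

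A recorded 3% (true 10%, 30% tested) would carry an interval of about 2.5% to 3.5%, far from 10%.

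**3. Two subgroups with the same true 10%**

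Assume 2,500 patients in each.
- 40% versus 60% tested: recorded 4% versus 6%, ratio 1.5. The standard error is √[(0.04×0.96 + 0.06×0.94)/2,500] = 0.00616; the pooled null value is the same to this precision. At two-sided 0.05, (0.02 − 1.96 × 0.00616)/0.00616 = 1.29, so the chance of a significant difference is 0.90. At 0.0007 it is 0.44.
- 20% versus 80% tested: recorded 2% versus 8%, ratio 4.0. The chance exceeds 0.99 even at 0.0007.
- For the 40% versus 60% contrast, the chance at 0.05 is 0.62 with a true rate of 5% and 0.98 with 15%.

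**4. Does a tested-only denominator solve it?**

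Suppose 30% are tested, tested patients have twice the risk of the untested, and the overall true rate is 10%.
- Risk in untested = 0.10/(0.30 × 2 + 0.70) = 7.7%
- Risk in tested = 2 × 7.7% = 15.4%
- All-patient recorded rate = 0.30 × 15.4% = 4.6%

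The tested-only figure is too high and the all-patient figure too low; neither equals 10%. If testing is unrelated to risk, the tested-only figure is correct (10%) and the all-patient figure reads 3%.

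**The case against.** The best defence is that much of this may be settled in material not shown. Table 1 is a summary, Section 6.4 points to the eCRF, and the CRF, its completion guidelines and the outcome definitions are Appendices 7, 8 and 11. These may already record whether a biomarker was taken and may limit MINS to noncardiac surgery. That stands, so the fix is conditional on it. But the appendices cannot make testing systematic, because Sections 2.2 and 6.5 rule out study procedures beyond the call and the questionnaire.

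A reader might also infer more than the text supports:
- *That the plan counts untested patients as event-free.* It does not say so. Section 7.3.3 refers to observed data, which is compatible with coding them as missing. Steps 1 to 3 of the working assume otherwise.
- *That a comparison of MINS or AKI between centres or nations is planned.* The Synopsis question on centres and nations concerns management practice. Section 2.9 (rationale) and Section 7.3.2 (nesting within centre, stratifying by country) make such use possible, but no section plans it. The planned outcome comparisons are by subgroup.
- *That centres would differ eightfold.* That is only the ratio of two chosen testing shares, 80% to 10%, and needs testing to be unrelated to risk.
- *That poorly controlled patients are tested more often.* Nothing in the protocol supports this.

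Incomplete detection is also common to routine-care cohorts, and only two components of one secondary endpoint are at issue. This bears on priority. It does not remove the case for recording who was tested.

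**Conclusion.** The point holds in a limited form. As planned, MINS and AKI incidences are rates of clinically detected events, and the protocol neither labels them so nor, in the text shown, collects what is needed to interpret them. Unless untested patients are identified, all-patient incidences are biased low, and differences across the planned subgroups partly reflect testing practice.

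The direction rests on the text plus the premise that these are laboratory-based diagnoses. It is firmer for MINS than for AKI, which may be partly recognised clinically. The size cannot be derived from the protocol. Under the stated assumptions a true 10% reads between 1% and 8%, and a modest imbalance in testing (40% versus 60%) is enough to create an apparent ratio of 1.5.

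The primary endpoint DAH-30 and 30-day mortality do not depend on this. It is a cheap improvement, not a threat to the study's main result.

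**What to change.** 1. Unless the eCRF already does so, add chart-extracted yes/no items at Day of Discharge in Table 1 and the eCRF: preoperative troponin measured, postoperative troponin measured, preoperative creatinine measured, postoperative creatinine measured.
2. In Sections 3.2 and 7.3.1, restrict MINS to noncardiac surgery.
3. In the same sections, report MINS and AKI in two ways: for all patients, labelled as clinically detected, and among tested patients. Put the proportion tested beside them, by subgroup, centre and country.
4. State that differences in these two endpoints will not be read as differences in risk without regard to testing.

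**Cost.** A few extra fields per patient and two denominators in the tables. No blood test is added and the observational design is unchanged. Neither figure is unbiased: the all-patient rate is low where testing is incomplete, and the tested-only rate has a smaller denominator and is high if higher-risk patients are tested more often. The testing fields need to be in place during data collection.

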## SYNOPSIS

Principal Investigator	[name] [name], Mater University Hospital, University College Dublin, Ireland
Title	Management and Outcome after Perioperative Care among European Diabetic Patients (MOPED)
Short Title	MOPED
Trial Registration	NCT04511312
Protocol Version	V 1.0
Background & Rationale	
Diabetes is common (about 20m patients in Europe), and patients have more surgical interventions than the general population. There are plausible pathophysiology and clinical mechanisms that diabetic patients are at increased risk of postoperative complications. When postoperative complications occur in the general population, they increase one-year mortality or major adverse events up to one year later. This is likely to be worse in diabetic patients. There is variation in practice guidelines in different countries in the perioperative management of diabetic patients undergoing major surgery, and whether this may affect postoperative outcome has not been investigated on a large scale. Neither is it known whether postoperative outcome differs depending on subgroups of diabetic patients, particularly whether different strata of preoperative glycaemic control affects outcome. If confirmed in this study, personalised perioperative management of diabetic patients may be enabled.

Objectives	
Main Objectives: To conduct the first major European epidemiological study on the perioperative management of diabetic patients undergoing surgery and their 30-day postoperative patient-centered outcome;
 
To evaluate subgroup outcomes, particularly strata of preoperative glycaemic control.
 
Specific Objectives: To address the following research questions: 1. What is the epidemiology of diabetic patients undergoing surgery across Europe: Are there major variations in perioperative glycaemic control? Does management practice vary between centres and between nations? 2. What is the extent and patient-centered impact of postoperative complications among diabetic patients up to 30 days after surgery in Europe? 3. To undertake sub-group analysis comparing these outcomes among *Diabetes Mellitus Type 1, Diabetes Mellitus Type 2, and other diabetic patients; *Patients with different strata (levels) of glycaemic control, i.e. HbA1c <53, HbA1c 53-69 and HbA1c >69 mmol.mol; *Patients who received different anaesthetic techniques: -Volatile versus total intravenous anaesthesia; regional versus general anaesthesia (GA) and

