Statistical Considerations	
Up to 5% of the population of Europe is thought to have diabetes. About 30m surgeries are performed in Europe per annum, therefore perhaps 1.5m diabetics have surgery in Europe per annum. It is proposed to evaluate a pragmatic sample of 5,000 European diabetic patients across at least 50 centres in a minimum of 10 nations.
 
Centres undertaking surgery for diabetic patients will be invited to contribute patients. It is envisaged that this target number would be enrolled over a two-year period from initial roll-out, with up to a further 12 months needed for final data acquisition, cleaning and analysis.
 
A sample size of 5,000 should be sufficient to avoid over-fitting and variance inflation for up to 63 factors or interactions. In addition, a sample size of 5,000 will have 90% power to find a small standardised difference of 0.10 as significant at <math>P < 0.05</math> for up to 63 independent hypotheses in comparing subsets of interest.

Risk-Benefit analysis	
There is no risk to patients participating in this study other than any risk associated with their perioperative care. Individual patients will not benefit from the study, but the knowledge gained from the overall evaluation will inform best practice in this previously under-researched field.

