## 7. STATISTICAL METHODOLOGY

### 7.1 Sample size estimation

It is proposed to evaluate a pragmatic sample of 5,000 European diabetic patients across at least 50 centres in a minimum of 15 nations. It is expected that this should be sufficient for the main epidemiological aspects of this study. It is envisaged that this target number would be enrolled over a two-year period from initial roll-out, with up to a further 12 months needed for final data acquisition, data cleaning and analysis. A sample size of 5,000 should be sufficient to avoid over-fitting and variance inflation for 50 to 70 factors and interactions based on the conventional square root or 100 values per variable respectively. In addition, a sample size of 5,000 will have at least 90% power to find a small standardized difference of

0.15 as significant at  $P < 0.05$  (Bonferroni corrected at  $P < 0.0007$ ) for up to 70 independent hypotheses and in comparing subsets of interest.

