### 7.3.4 Ancillary analyses

In addition to the sensitivity analyses as described, the effects of pre-defined subsets will be investigated. These subsets will include: DM1, DM2, DM3, MODY and LADA diabetic patients; Strata of glycaemic control, HbA1c <53, HbA1c 53-69 and HbA1c >69 mmol/mmol;

Anaesthetic techniques, inhalational (IA) versus total intravenous (TIVA), regional (RA) versus general (GA), combined GA and RA versus GA alone.

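### The Synopsis and section 7.1 imply different significance thresholds (0.05 and 0.0007), and section 7.3 does not say which one governs

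*Protocol*

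**What the plan says.** Three places in the protocol bear on what counts as a significant result.

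- **Synopsis, Statistical Considerations.** 5,000 patients are said to give 90% power for a standardised difference of 0.10 at P<0.05, "for up to 63 independent hypotheses in comparing subsets of interest". No corrected level is shown.
- **Section 7.1.** The same 5,000 patients are said to give at least 90% power for a standardised difference of 0.15 at P<0.05, "Bonferroni corrected at $P < 0.0007$ ) for up to 70 independent hypotheses and in comparing subsets of interest".
- **Section 7.3.** Section 7.3.1 opens with a descriptive aim ("The aim of this research is to describe and quantify the epidemiology of the perioperative management of diabetic patients in Europe") and 95% confidence intervals. It then plans univariate screening and stepwise selection, and says that "Robust multivariable regressions using maximum likelihood estimation (MLE), including Poisson and negative binomial, will be used to identify significant associations". Section 7.3.4 adds that "In addition to the sensitivity analyses as described, the effects of pre-defined subsets will be investigated". Neither section gives a significance level or refers back to 7.1.

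The comparisons come from section 3.1 ("To undertake sub-group analysis comparing these outcomes among" diabetes types, HbA1c strata and anaesthetic techniques). That section places the list of hypotheses in Appendix 9, which is not in the text at hand.

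**The concern.** The two power statements describe the same study and sample but differ in effect size (0.10 against 0.15), number of hypotheses (63 against 70) and the level shown (0.05 against 0.0007). If both led to the same decision rule, this would be a drafting slip. They do not: the Synopsis power figure can be reached only without a correction, whereas 7.1 applies one.

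Since 7.3 is silent, an analyst could follow either passage and cite the protocol in support. The results affected are small differences between subsets, which are the effects that both statements say the study is sized to detect. The subset results are also meant to carry weight: the Synopsis lists among its main objectives "To evaluate subgroup outcomes, particularly strata of preoperative glycaemic control", and section 2.9 ties a confirmed association with poor preoperative control to the start of personalised perioperative care.

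**Working it through.** **Inputs.** From the Synopsis: N = 5,000, difference 0.10, P<0.05, 63 hypotheses, 90% power. From 7.1: N = 5,000, difference 0.15, level 0.0007, 70 hypotheses, at least 90% power. Assumed, because the protocol does not state them: two equal groups of 2,500, two-sided tests, standard deviation 1, no clustering by centre, and independent tests for the family-wise figures.

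**Formulae.** The standard error of a standardised difference is √(1/2500 + 1/2500) = 0.02828. Power is Φ(d/0.02828 − z), where z is the two-sided critical value.

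**1. Section 7.1 reproduces.** 0.05/70 = 0.000714, which rounds to 0.0007, so z = 3.390. Power = Φ(0.15/0.02828 − 3.390) = Φ(5.303 − 3.390) = Φ(1.914) = 97.2%. The claim of at least 90% is met; 90% would need 3,880 patients in total.

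**2. The Synopsis reproduces only without a correction.** Here d/SE = 0.10/0.02828 = 3.536.

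| Level | z | Power for 0.10 | Total N for 90% |
|---|---|---|---|
| 0.05, uncorrected | 1.960 | Φ(1.576) = 94.2% | 4,204 |
| 0.05/63 = 0.00079 | 3.355 | Φ(0.180) = 57.2% | 8,600 |

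One-sided testing at 0.05/63 raises power only to 64.7%. So either the Synopsis intends 0.05 for each test and conflicts with 7.1 on the threshold, or it intends a correction and its 90% is wrong.

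**3. The zone where the two readings disagree.** The smallest observed difference that reaches significance is z × 0.02828:
- at 0.05: 1.960 × 0.02828 = 0.055
- at 0.0007: 3.390 × 0.02828 = 0.096

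Observed differences between these values are significant at 0.05 and not at 0.0007. For groups of 2,500 and 750 (assumed sizes), the standard error is √(1/2500 + 1/750) = 0.0416, and the zone is 0.082 to 0.141.

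**4. What the choice of level does to false positives.** Family-wise error for m independent tests at level a is 1 − (1 − a)^m.

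| Tests | At 0.05 each | At 0.0007 each |
|---|---|---|
| 5 (DAH-30 across the five comparisons in 3.1) | 22.6% | 0.35% |
| 70 (the number in 7.1) | 97.2% | 4.8% |

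Expected false positives over 70 tests are 70 × 0.05 = 3.5, against 70 × 0.0007 = 0.05.

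**The case against.** The strongest reply is that 7.1 does state a corrected level and explicitly extends it to subset comparisons, so a fair reader would apply 0.0007 in 7.3. That answers much of the worry about error rates.

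A reader might infer something stronger: that DAH-30 has no primary comparison, so false-positive subgroup findings are likely. The documents do not support this, for four reasons.

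- **The level in 7.1 controls the error.** At 0.0007, family-wise error is 4.8% for 70 independent tests.
- **The count of tests need not exceed 70.** The 13 outcomes named in 7.3.1 across the five comparisons in 3.1 make 65. A larger family comes from pooling the outcome lists of 3.2 and 7.3.1 (15 outcomes) and testing all nine pairwise contrasts. That makes 135 tests, which no section plans, and even then independent tests at 0.0007 give 9.0%.
- **A descriptive cohort needs no single confirmatory contrast.** It can estimate DAH-30 as its primary endpoint with confidence intervals.
- **A hierarchy or exploratory labels may exist elsewhere.** Appendix 9 or the statistical analysis plan may supply them, and neither is at hand.

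Those points stand. What they do not remove is the contradiction within the protocol. A list of hypotheses in Appendix 9 would not make the Synopsis power correct at a corrected level, and nothing in 7.3 tells the analyst to prefer 7.1 to the Synopsis. Univariate and stepwise selection adds a separate difficulty, since P values taken after selection do not keep their nominal level, whether 0.05 or 0.0007.

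**Conclusion.** The point holds as an inconsistency in the stated threshold and power. The Synopsis claim of 90% power for 0.10 is true only at an uncorrected 0.05 (94.2%) and falls to 57.2% at 0.05/63. Section 7.1 is internally sound at equal groups (97.2% for 0.15 at 0.0007). Because 7.3 does not choose between them, results with P between 0.0007 and 0.05 have no settled status; at 2,500 against 2,500 these are observed differences of about 0.055 to 0.096.

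False positives are likely only if 0.05 is applied to each test: 23% over five independent DAH-30 tests and 97% over 70. At 0.0007 the rate over 70 is about 5%. Correlation between tests would lower these family-wise rates.

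The power figures depend on the equal split. With N = 5,000, power for 0.15 at 0.0007 stays at or above 90% only while the smaller group holds at least about 26% of patients. Clustering by centre would change power further.

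**What to change.** 1. **Synopsis.** Replace the power sentence with the figures of 7.1 (difference 0.15, 70 hypotheses, corrected level 0.0007). Alternatively, keep 0.10 and state its power at the corrected level: about 57% at 0.05/63, or Φ(3.536 − 3.390) = Φ(0.146), about 56%, at 0.0007. Either way, the Synopsis and 7.1 should end with the same number of hypotheses and the same level.
2. **Sections 7.3.1 and 7.3.4.** State that, for the pre-defined hypotheses and subset comparisons, significant means below the corrected level in 7.1.
3. **Section 7.3.1.** State that associations found through univariate or stepwise selection, or lying outside the pre-defined list, are reported as exploratory estimates with 95% confidence intervals and without a claim of significance.

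Naming DAH-30 by HbA1c stratum as a single primary comparison is an option for the sponsor. It is not needed to remove the contradiction.

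The cost is a few sentences, with no new data, patients or procedures. The small downside is that fewer associations can be called significant.
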